8.1.1. Screening Period—Within 28 Days Prior to Randomization/ Treatment (Day -28 to -1)

8.1.1.1. Visit 1—All Subjects

Note: All ophthalmic procedures (including imaging) are to be performed on both eyes, except where specified.

Before any study-specific procedures are performed, the purpose and nature of the study should be explained and the patient should read, sign, and date the Institutional Review Board/Independent Ethics Committee (IRB/IEC)-approved Informed Consent Form (ICF). The individual obtaining consent from the patient and a witness, if applicable, should also sign and date the ICF. Once the patient has signed the ICF, a screening number should be assigned to the patient. Demographic information, significant medical/surgical history within the previous 5 years, invasive ocular procedures within the previous 5 years, and concomitant medications used within 30 days prior to screening should be collected (including vitamins and all over-the-counter as well as prescription medications). Complete smoking/ tobacco history should also be collected.

Subject eligibility should then be determined by reviewing the inclusion/exclusion criteria and the study eye should be selected. Prior to the administration of fluorescein, blood and urine should be collected for safety labs (including blood for human chorionic gonadotropin/follicle-stimulating hormone/luteinizing hormone [HCG/FSH/LH], if applicable) and vital signs along with a physical examination including weight and height should be performed.

A complete ophthalmic exam including slitlamp exam of the cornea, iris, anterior chamber, aqueous reaction (cells and flare), dilated fundus exam of the vitreous and retina, and intraocular pressure (IOP) measurement. Normal luminance BCVA should be performed prior to dilating the eyes. Images should be captured as outlined in the Visit Schedule (FAF, NIR, DCFP, FFA) and forwarded to the reading center for determination of eligibility if applicable.

Mesopic microperimetry should be performed on both eyes post dilation of the eyes and forwarded to the reading center.

8.1.2. Randomization/ Initial Treatment—Day 1—Within 28 Days of Screening

8.1.2.1. Visit 2—All Groups

At this visit, all inclusion/exclusion criteria should be reviewed prior to randomization and dosing, including the determination of eligibility by the reading center. Subjects will be randomized using the Interactive Web Response (IWR) System. A complete ophthalmic exam including slitlamp exam of the cornea, iris, anterior chamber, lens, and aqueous reaction (cells and flare), dilated fundus exam of the vitreous and retina, and IOP measurement will be performed and imaging collected as per the Visit Schedule.

All assessments should be performed on the same day. All study visits should be scheduled and projected based on the Day 1 visit date.

Blood should be drawn for anti-pegcetacoplan antibodies.

Prior to dilating the eyes, all functional tests should be performed (NL-BCVA, LL-BCVA, and MNREAD or Radner Reading Charts [in select countries]). Subjects at select sites will be trained on how to use the home-based digital applications for visual function and reading speed if the subject decides to participate in this portion. This training must occur after completion of all functional tests (NL-BCVA, LL-BCVA). Tests completed using the digital application at select sites (optional) should be completed prior to dilating the eyes but after completion of all functional tests and quality of life measures (NL-BCVA, LL-BCVA, MNREAD or Radner Reading Charts [in select countries], NEI VFQ-25, and FRI). The subject should be instructed to take the electronic device home and to complete the digital application weekly on the same day each week, if possible. The quality of life measures (NEI VFQ-25 and FRI) should be administered by the masked site staff.

Imaging should be performed including FAF, SD-OCT, OCT-A (select sites), endothelial cell count (select sites) and NIR and sent to the reading center for evaluation.

Study drug or sham injection should be performed by the unmasked physician as described in the manual of procedures and the study eye should be monitored post injection as outlined in Section 9.16. A follow-up phone call should be scheduled with the subject 4 ± 2 days after randomization Day 1 to assess for any AEs.

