7.3.2. Treatment Administration

Only qualified study staff and those delegated the responsibility of study drug administration on the delegation of authority log should perform this procedure. All staff should be appropriately trained on all procedures prior to performing the procedures. Sites should follow the Visit Schedule for order of procedures and assessments.

Administration of study treatment (pegcetacoplan or sham) can be done on a separate day from the assessment visit if both days fall within the visit window. If this occurs on the randomization

visit, then the administration of pegcetacoplan or sham should be done within 3 days of randomization and after approval from the medical monitor. When study treatment administration is on a day other than a study visit, then the only assessment that must be done on the day of study treatment administration is the IOP preinjection.

If a subject falls outside the visit window for a dosing visit, the dose should be skipped and the subject should be scheduled on time for the next dosing visit.

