8. STUDY PROCEDURES

A study schema is presented below in Figure 1. All randomized subjects will return every month to the clinical site for assessments and additional pegcetacoplan or sham injections according to their randomization scheme until Month 12. From Month 12 onwards, subjects will return to the clinical site based on their randomized treatment schedule (monthly or EOM) and will follow the treatment regimen and assessments outlined in the Visit Schedule until Month 24. In addition, subjects will be contacted via phone by masked study staff 4 (±2) days after the first 3 study treatments to collect safety information.

The end of this trial for each subject is defined as when the subject completes their Month 24 study visit, approximately 30 days (monthly treatment group) and approximately 60 days (EOM treatment group) after the last visit at which IP is administered. The period following the last dose of IP is sufficient to evaluate the safety of pegcetacoplan based on its half-life in the vitreous; further details can be found in the pegcetacoplan IB. At the end of the 24-month study period, subjects will be offered entry to enroll into a separate open-label study.

Figure 1: Study Schema

Abbreviations: PM= pegcetacoplan monthly; SM= sham monthly; PEOM= pegcetacoplan every-other-month; SEOM= sham every-other-month.

Subjects who discontinue study treatment should return to the clinic for study assessments as per the outlined visit schedule for their assigned treatment arm.

Safety will be assessed throughout the study by a number of evaluations including: monitoring of AEs, preinjection and postinjection monitoring, blood and urine samples will be collected, physical examination, vital signs, and follow-up phone calls will be performed. Blood samples will also be collected for anti-therapeutic antibodies, genotyping, and clinical repository (if the subject consents to this portion).

The planned length of participation in the study for each subject is approximately 25 months (from the beginning of the screening period through completion of the Month 24 visit). After completion of the 24-month treatment period, subjects will be offered entry into a separate openlabel study.

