8.1. Study Visit Schedule

Below is a condensed description of the study visits and the procedures and examinations that will be performed. Please refer to the Visit Schedule in Appendix A to Appendix D for a detailed schedule of procedures/assessments for the monthly and EOM visit schedules. Additional safety assessments not listed in this section or the flow chart may be performed if considered necessary at the discretion of the investigator.

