8.1.3. Treatment Phase—24 Months

8.1.3.1. Months 1-12

8.1.3.1.1. Visits 3-14 (Monthly and Every-Other Month Group)

During this phase, there will be clinic visits every month. Dosing and assessments will occur monthly in the monthly pegcetacoplan and sham injection treatment arms. Dosing will occur every other month in the EOM pegcetacoplan and sham injection treatment arms, however, the subjects will return monthly for assessments (with no dose given).

A complete ophthalmic exam including slitlamp exam of the cornea, iris, anterior chamber, lens, and aqueous reaction (cells and flare), dilated fundus exam of the vitreous and retina, and IOP measurement will be performed and imaging collected as per the Visit Schedule.

Blood will be drawn for safety labs, anti-pegcetacoplan antibodies, and genotyping (Month 2 only) prior to the administration of fluorescein as per the Visit Schedule. Samples will be collected for the clinical repository for those subjects that consent to this portion.

Prior to dilating the eyes, all functional tests will be performed (NL-BCVA, LL-BCVA, and MNREAD or Radner Reading Charts [in select countries]). Tests completed using the digital application at select sites (optional) will be completed prior to dilating the eyes but after completion of all functional tests and quality of life measures (NL-BCVA, LL-BCVA, MNREAD or Radner Reading Charts [in select countries], NEI VFQ-25, and FRI). At select sites the subject should be instructed to take the electronic device home and to complete the digital application weekly on the same day each week, if possible. The subject will be instructed to bring back the electronic device for the visits specified in the schedule of events. The quality of life measures (NEI VFQ-25 and FRI) will be administered by the masked site staff.

Mesopic microperimetry should be performed on both eyes (where specified) post dilation of the eyes and forwarded to the reading center.

Imaging will be performed including FAF, FFA, SD-OCT, OCT-A (select sites), endothelial cell count (select sites) and NIR and sent to the reading center for evaluation per the visit schedule.

Study drug or sham injection should be performed by the unmasked physician as described in the manual of procedures and the study eye should be monitored post injection as outlined in Section 9.16. A follow-up phone call should be scheduled with the subject as outlined in the schedule of events.

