- P. Postinjection assessments should be performed within 5 minutes after dosing by the unmasked physician or study staff and should include a gross assessment of vision (finger-counting, hand-motion, then light perception when applicable). If subject passes gross vision test, the subject may leave the site. If subject fails gross vision test, the tonometry should be performed. IOP should be ≤30 mm Hg in order for the subject to leave the site. If necessary, antiglaucomatous medication can be given to lower the IOP. If IOP is >30 mm Hg, assessments will continue every approximately 30 minutes from the previous measurement until the subject passes gross vision test and IOP is ≤30 mm Hg. Note: if the study eye is treated with a ranibizumab or aflibercept injection during the same visit as the study treatment (pegcetacoplan or sham), the treatment with ranibizumab or aflibercept must be performed first. The pre- and post- anti-VEGF IOP values must be measured and recorded on the eCRF.
- Q. Starting at Day 1, study subjects will be contacted by study site staff within 4 ± 2 days after each study treatment visit (through Month 3) to collect any information on any safety concerns, decrease in vision, eye pain, unusual ocular events, or any new ocular symptoms in the study eye. If the physician determines that there are any safety concerns, a follow-up visit should be scheduled as soon as possible.
- R. Record concomitant medications (ie, prescription and over-the-counter medications) used by the patient within 30 days of screening and throughout the subject's participation in the study.
- S. In addition to the time points indicated on the study schedule, OCT-A should be performed at the time of any suspected new active CNV. If new active CNV is confirmed in the study eye, OCT-A should be repeated every 2 months for the study eye.

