- T. Administration of pegcetacoplan or sham can be done on separate days from the assessment visit if both days fall within the visit window. Administration of study treatment (pegcetacoplan or sham) can be done on a separate day from the assessment visit if both days fall within the visit window. If this occurs on the randomization visit, then the administration of pegcetacoplan or sham should be done within 3 days of randomization and after approval from the medical monitor. When study treatment administration is on a day other than a study visit, then the only assessment that must be done on the day of study treatment administration is preinjection IOP.

APPENDIX B: VISIT SCHEDULE—Monthly Group—Month 13 to Month 24

	Treatment												
Visit #	15	16	17	18	19	20	21	22	23	24	25	26	1
Day	390	420	450	480	510	540	570	600	630	660	690	720	Early
Week	52	56	60	64	68	72	76	80	84	88	92	96	Term ^A
Month	13	14	15	16	17	18	19	20	21	22	23	24	1
Window (+ or – days)	8	8	8	8	8	8	8	8	8	8	8	8	
Informed consent / assign screening number													
Demographic data													
Inclusion/exclusion criteria ^B													
Medical/surgical/ocular history ^C													
Blood draw—safety labs D,E,F						x						x	x
Urine sample collection ^{D,E,F}						X						X	X
Urine pregnancy test ^{D,E,F}	x	X	X	X	X	x	X	X	X	X	X	X	
Blood draw—anti-pegcetacoplan Ab ^D		X				X						X	X
Blood draw—genotyping (if applicable) ^D													
Blood draw for clinical repository (if applicable) ^{D,G}												x	x
Vital signs ^H	x	X	X	x	X	x	X	x	x	x	X	x	x
Physical examination ^I												X	X
BCVA ^J	x	X	X	X	X	X	X	X	X	X	X	X	X
LL-BCVA I	x	X	X	X	X	X	X	X	X	X	X	X	x
MNREAD or Radner Reading Charts (select countries) ^{J,K}						x						x	x
Mesopic microperimetry ^L						SE						X	x
Slitlamp examination	X	X	X	X	X	X	X	X	X	X	X	X	X
Endothelial cell count ^S												X	X
NEI VFQ-25 M						X						X	X
FRI M						X						X	X
Dilated Indirect Ophthalmoscopy	X	X	X	X	X	X	X	X	X	X	X	X	X
Home-based digital applications M,N,S						X						X	
IOP measurement	X	X	X	X	X	X	X	X	X	X	X	X	X
SD-OCT O	x	X	X	X	X	X	X	X	X	X	X	X	x

		Treatment												
Visit #	15	16	17	18	19	20	21	22	23	24	25	26]	
Day	390	420	450	480	510	540	570	600	630	660	690	720	Early	
Week	52	56	60	64	68	72	76	80	84	88	92	96	Term ^A	
Month	13	14	15	16	17	18	19	20	21	22	23	24]	
Window (+ or – days)	8	8	8	8	8	8	8	8	8	8	8	8		
FAF ⁰		SE		SE		X		SE		SE		X	X	
NIR ⁰		SE		SE		X		SE		SE		X	X	
DCFP O												X	x	
FFA ⁰												X	X	

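### The first safety call is timed from randomization although the first injection may come up to 3 days later, and Section 8 counts 3 calls where the monthly schedule has 4

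*Protocol*

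**What the plan says.** The protocol times the post-treatment safety call in three ways.

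- Section 8, for all subjects, has masked staff telephone 4 (±2) "days after the first 3 study treatments to collect safety information". The time origin is the treatment.
- Section 8.1.2.1, on the Day 1 visit, says: "A follow-up phone call should be scheduled with the subject 4 ± 2 days after randomization Day 1 to assess for any AEs". The time origin is randomization.
- Footnote Q of Appendix A (monthly groups) places calls 4 ± 2 "days after each study treatment visit (through Month 3"). Appendix C (EOM groups) uses the same wording through Month 4. The time origin is a visit.

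Section 7.3.2 and footnote T let the visit and the injection be separated: "Administration of pegcetacoplan or sham can be done on separate days from the assessment visit if both days fall within the visit window". For the first dose, the injection "should be done within 3 days of randomization and after approval from the medical monitor".

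On the number of calls, Section 8 gives 3 for everyone. The call row in Appendix A is marked at Day 1 and Months 1, 2 and 3. In Appendix C it is marked at Day 1 and Months 2 and 4. For Visits 3 to 14, Section 8.1.3.1.1 defers to the schedule: "A follow-up phone call should be scheduled with the subject as outlined in the schedule of events".

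**The concern.** The call is a scheduled check in the days after an injection. Section 4.2 places the risk of sterile or infectious intraocular inflammation in exactly those days. A call made before the first injection cannot serve that purpose, and Section 11.2 would class anything it picked up as a pretreatment event.

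Section 8.1.2.1 is where a site looks for what to do at Visit 2. It does not say that the call moves when the injection moves. The Amendment 3 history records that separate-day dosing was added to Section 7.3.2 and lists no change to the call wording in Section 8.1.2, which may be how the mismatch arose.

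Footnote Q has a related weakness. Footnote T describes a separate-day injection in these terms: "When study treatment administration is on a day other than a study visit, then the only assessment that must be done". If such an injection is not on a study visit, the *study treatment visit* in footnote Q does not clearly mean the injection day.

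**Working it through.** **Inputs.** Call window of 2 to 6 days after its time origin (4 ± 2; Sections 8 and 8.1.2.1). First-dose deferral *d* of 0 to 3 days after randomization (Section 7.3.2, footnote T). Call marks as in Appendices A and C.

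**First call.** All days in the formulas are counted from randomization.

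- Section 8.1.2.1 allows the call on days 2 to 6.
- Section 8 allows it on days *d* + 2 to *d* + 6.
- Gap from injection to call under Section 8.1.2.1 alone: (2 − *d*) to (6 − *d*), nominally 4 − *d*.
- Days that satisfy both sections: *d* + 2 to 6.

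| Deferral *d* | Gap under 8.1.2.1 alone (days after injection) | Nominal gap | Call days allowed by Section 8 | Call days meeting both |
|---|---|---|---|---|
| 0 | 2 to 6 | 4 | 2 to 6 | 2 to 6 |
| 1 | 1 to 5 | 3 | 3 to 7 | 3 to 6 |
| 2 | 0 to 4 | 2 | 4 to 8 | 4 to 6 |
| 3 | −1 to 3 | 1 | 5 to 9 | 5 to 6 |

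With no deferral the two sections agree. At 3 days, a call that follows Section 8.1.2.1 can come 1 day before the injection and no later than 3 days after it. The nominal day-4 call never precedes the dose, and it drops below the 2-day minimum only at the 3-day deferral. The last column is never empty, so a site that reads both sections can always comply with both.

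**Later calls.** Section 8 fixes the time origin for the first 3 treatments.

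- Monthly groups, on schedule: these are Day 1, Month 1 and Month 2. The Month 3 call therefore rests on footnote Q alone.
- EOM groups, on schedule: these are Day 1, Month 2 and Month 4, so no call rests on footnote Q alone.

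**Count.**

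| Groups | Section 8 | Schedule |
|---|---|---|
| Monthly | 3 | 4 (Visits 2, 3, 4, 5) |
| EOM | 3 | 3 (Visits 2, 4, 6) |

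The figure in Section 8 is reproduced for the EOM groups only.

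**The case against.** Four objections carry weight.

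1. **Section 8 binds as well.** A call made before the first injection breaches Section 8, so the protocol as a whole does not permit it, and the table shows that both rules can always be met. This stands. The defect is that one operative section, read alone, allows a mistimed call. The instructions are not impossible to reconcile.
2. **Context of Section 8.1.2.1.** Its parent heading ties randomization and initial treatment to Day 1, and the call sentence follows the injection instruction. Deferral is an exception that needs approval. This also stands and limits how often the case can arise.
3. **Footnote Q.** *Study treatment visit* can naturally mean the visit at which treatment is given, especially in the EOM schedule, where some visits have no dose. This largely stands, and footnote T leaves only an ambiguity. A reader might go further: take footnote Q to mean the assessment day, place assessment and injection at opposite ends of the ±8-day window, and infer that every compliant call at later visits would precede the injection. The documents do not support that. It needs the less natural reading of footnote Q together with an extreme separation, and it ignores Section 8 for the first 3 treatments.
4. **The count.** Section 8.1 sends sites to the appendices for detail ("Please refer to the Visit Schedule in Appendix A to Appendix D for a detailed schedule of procedures/assessments"), and Section 8.1.3.1.1 does the same for the later calls. A site that follows the schedule loses no call. The mismatch is one to harmonize, with little practical effect.

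There are other safeguards too: the check within 5 minutes of injection (Section 9.15), regular examinations with adverse event collection in the first year, and unscheduled visits (Section 8.1.5).

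**Conclusion.** The inconsistency is real and minor. Section 8.1.2.1 uses the wrong time origin for a post-injection check whenever the first dose is deferred. At the 3-day limit, the permitted window shifts from 2 to 6 days after the injection to between 1 day before and 3 days after it. Footnote Q is ambiguous for separate-day dosing, and this matters most for the monthly Month 3 call. Section 8 understates the monthly call count by one.

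These figures are bounds on permitted timing. The documents do not say how often doses are deferred, and the manual of procedures, which may say more, is not available here. Same-day dosing is the default.

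A reader might infer that the planned safety results are at risk. They are not. Adverse events are also collected at the scheduled visits, and SAP Section 7.1 defines treatment emergence by onset or worsening relative to the first dose, without reference to the call. No efficacy analysis is touched.

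**What to change.** - **Section 8.1.2.1:** time the call *4 ± 2 days after the first injection*.
- **Section 8:** replace the single count with *the first 4 study treatments (monthly groups) or the first 3 (EOM groups)*. Aligning to the schedule keeps every call now planned.
- **Footnote Q of the Day 1 to Month 12 schedules** (Appendices A and C and their COVID-19 versions in Appendix K): replace *study treatment visit* with *study treatment administration*.

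Only these four copies of footnote Q govern visits with a call. The call row is blank in the Month 13 to 24 schedules, and the SAP only reproduces the schedules, so those copies can follow at a routine revision.

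The cost is wording only: two sentences and one phrase in four places, or a short memo to sites until the next amendment. Once calls are timed from the injection, each one falls 2 to 6 days after the dose it is meant to check, whatever the deferral.

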8.1.3. Treatment Phase—24 Months

8.1.3.1. Months 1-12

8.1.3.1.1. Visits 3-14 (Monthly and Every-Other Month Group)

During this phase, there will be clinic visits every month. Dosing and assessments will occur monthly in the monthly pegcetacoplan and sham injection treatment arms. Dosing will occur every other month in the EOM pegcetacoplan and sham injection treatment arms, however, the subjects will return monthly for assessments (with no dose given).

A complete ophthalmic exam including slitlamp exam of the cornea, iris, anterior chamber, lens, and aqueous reaction (cells and flare), dilated fundus exam of the vitreous and retina, and IOP measurement will be performed and imaging collected as per the Visit Schedule.

Blood will be drawn for safety labs, anti-pegcetacoplan antibodies, and genotyping (Month 2 only) prior to the administration of fluorescein as per the Visit Schedule. Samples will be collected for the clinical repository for those subjects that consent to this portion.

Prior to dilating the eyes, all functional tests will be performed (NL-BCVA, LL-BCVA, and MNREAD or Radner Reading Charts [in select countries]). Tests completed using the digital application at select sites (optional) will be completed prior to dilating the eyes but after completion of all functional tests and quality of life measures (NL-BCVA, LL-BCVA, MNREAD or Radner Reading Charts [in select countries], NEI VFQ-25, and FRI). At select sites the subject should be instructed to take the electronic device home and to complete the digital application weekly on the same day each week, if possible. The subject will be instructed to bring back the electronic device for the visits specified in the schedule of events. The quality of life measures (NEI VFQ-25 and FRI) will be administered by the masked site staff.

Mesopic microperimetry should be performed on both eyes (where specified) post dilation of the eyes and forwarded to the reading center.

Imaging will be performed including FAF, FFA, SD-OCT, OCT-A (select sites), endothelial cell count (select sites) and NIR and sent to the reading center for evaluation per the visit schedule.

Study drug or sham injection should be performed by the unmasked physician as described in the manual of procedures and the study eye should be monitored post injection as outlined in Section 9.16. A follow-up phone call should be scheduled with the subject as outlined in the schedule of events.

In the event that a subject is early terminated from the study, all early termination procedures should be performed even if they are outside the allowed study window.

If the subject would like to discontinue dosing but is amenable to continuing in the study, the site should make every effort to have the subject complete as many follow-up visits as possible.

